4.3 Subject and Trial Discontinuation

Subjects may choose to withdraw from this study at any time for any reason without penalty of jeopardizing their health care or loss of benefits to which the subject is otherwise entitled.

Within the provisions of informed consent and good clinical judgment with respect to safety, every attempt will be made to have subjects complete the study. Reasons for subject discontinuation include, but are not limited to the following:

- 1. Subject experiences an AE that in the judgement of the Investigator poses a significant risk to the subject for continued participation in the study.
- 2. Subject uses a prohibited medication (listed in Section 5.7) that in the judgment of the Investigator poses a significant risk to the subject for continued participation in the study or that will interfere with the interpretation of the results of the study.
- 3. Subject becomes pregnant.
- 4. Significant protocol violation or noncompliance on the part of the subject or the Investigator.
- 5. Intercurrent illness that requires treatment that is not consistent with the protocol requirements, or intercurrent illness or the associated treatment that in the judgment of the Investigator poses a significant risk to the subject for continued participation in the study.
- 6. Episodes of hypoglycemia not responsive to changes in diet or dose regimen (Section 7.3.1)
- 7. Subject meets one of the exclusion criteria during the study
- 8. Subject wishes to withdraw for any reason.
- 9. Sponsor elects to end the study, or the Investigational Site elects to end the study at their site.
- 10. Any other reason that in the judgment of the Investigator poses unacceptable risk to the subject.

Subjects who withdraw from the study prior to treatment may be replaced. Subjects who are withdrawn and have received at least one treatment will not be replaced.

Except in cases of emergency, the Investigator should consult with the Sponsor and the Medical Monitor before removing the subject from the study. In some circumstances, it may be necessary to temporarily interrupt treatment as a result of AEs that may have an unclear relationship to study treatment. The investigator should obtain approval from the Sponsor and Medical Monitor before restarting study treatments that were temporarily discontinued for an AE.

In the event that a subject discontinues the study prior to completion, the date the subject is withdrawn and the reason for discontinuation will be recorded in the source documents and eCRF. Although a subject will not be obliged to give his/her reason for withdrawing prematurely, the investigator will make a reasonable effort to obtain the reason while fully respecting the subject's rights.

All subjects who are randomized and treated (i.e., received any amount of study treatment) will be included in the safety analyses. Thus, every effort will be made to contact any subject who fails to attend any follow-up appointments/contacts, in order to ensure that he/she is in satisfactory health. If a subject withdraws from the study as a result of meeting discontinuation criteria (Section 4.3) after the start of study treatment administration, reasonable efforts should be made to have the subject return for the early withdrawal evaluations (Section 3.8). Any subject withdrawn due to a

suspected study treatment -related AE should be followed until resolution or stabilization of the event.

If a subject becomes pregnant, study treatment will be discontinued immediately. The subject will be followed until delivery or other termination of pregnancy for outcome.

The Sponsor has the right to terminate this study, and the Investigator/Investigational Site has the right to close the site, at any time, although this should occur only after consultation between involved parties. The Investigator will notify the IRB in writing of a premature termination of a study or closure of Investigational Site, and will send a copy of the notification to the Sponsor.

Events that may trigger premature termination of a study or closure of an Investigational Site include, but are not limited to, a new toxicity finding, a request to discontinue the trial from a regulatory authority, non-compliance with the protocol, GCP violations, slow recruitment/low enrollment, or change in development plans for the study treatment.

If either of the criteria listed below is met, enrollment of new subjects and dosing of ongoing subjects will be temporarily stopped. The Investigator, Sponsor, and the Medical Monitor will discuss whether a lower dose or any additional treatment guidelines should be implemented, or if the trial should be permanently stopped. Any proposed changes to the protocol to address such findings will be submitted for review and approval by the IRB and FDA prior to re-starting the trial.

- 1. A death within 30 days after study treatment administration where there is a reasonable possibility that the drug caused the event;
- 2. Two Grade 4 AEs where there is a reasonable possibility that the study treatment caused the events.

5 STUDY TREATMENT

5.1 Description of Investigational Drug

Active:

Code name: ORMD-0801

Dosage form Cohort A: 2 soft gel capsules per dose (1 may be placebo as needed for blinding)

Dosage form Cohort B: 1 soft gel capsule per dose (may be placebo as needed for blinding)

Strength: 8 mg insulin per capsule or 16 mg insulin per capsule

Description: API (recombinant human insulin USP), in Oramed's proprietary formulation [SBTI, disodium EDTA, fish oil, aerosil, and TWEEN 80] in capsules.

Placebo control:

Fish oil in capsules, identical in appearance to ORMD-0801

Exipient-matched placebo control:

SBTI, disodium EDTA, fish oil, aerosil, and TWEEN 80, identical in appearance to ORMD-0801

5.1.1 Packaging and Labeling

All study medication will be shipped in pre-prepared kits to be allocated to subjects by the IWRS based on study period, randomization and individual dose regimen achieved. Study medication will be distributed at each visit sufficient to cover the time between visits. The investigational site pharmacist or designee will be responsible for dispensing the appropriate treatment period study treatment based on the randomization schedule.

Shipments of study medication for the double-blinded treatment period will be received in blinded packages. Study medication will be dispensed to the site with instructions for when treatment can be administered and with a diary for recording administration of study medication. Medication containers and any unused capsules will be retained at the study site after the treatment phase of the trial is complete. Unused study medication will be returned to the manufacturer for destruction.

The treatment packages will be labeled with the following information:

- Study number
- Kit No./Bottle ID
- Dosage Form/Content
- Directions for use, including route of administration
- Number of capsules in package
- Storage conditions
- Instructions to "keep out of reach of children"
- Caution: New Drug Limited by Federal (or United States) law to investigational use.
- Name of Sponsor

A separate label with the identical information will be provided with the label on the package for drug accountability purposes.

5.1.2 Storage and Handling

All study treatment must be kept in an appropriate, secure area to prevent unauthorized access. The study treatment is to be shipped under refrigerated conditions and stored in the original packaging at controlled temperature (36 to 46°F; 2 to 8°C). Excessive humidity should be avoided. Storage conditions will be monitored and appropriate monitoring logs maintained as source data. Deviations from the established temperature, as well as the occurrence of excessive humidity, should be documented, and the Sponsor should be notified. Study treatment should be handled using proper procedures as defined by investigational site standard operating procedures (SOPs) for Investigational Drugs. Unused study medication will be returned to the manufacturer for destruction.

5.2 Randomization

Of the total 360 subjects, 265 subjects will be randomized to Cohort A and receive ORMD-0801 or placebo in one of 3 treatment regimens: QHS, BID, or TID. The actual treatment (ORMD-0801 or placebo) will be double-blinded to the subjects, investigators, monitors, and staff members responsible for treating and evaluating subjects, but the treatment regimen will be unblinded.

Creation, maintenance, and communication of the randomization scheme will be managed by an interactive web-based response system (IWRS). Subjects will be randomized 1:1:1 to QHS, BID, or TID and 1:3 (placebo:ORMD-0801) within each of those regimens at Visit 3. Therefore the overall randomization will be 1:1:1:1 (all placebo dosing regimens combined: ORMD-0801 QHS: ORMD-0801 BID: ORMD-0801 TID). Randomization will be in block sizes of 12 (1:3;1:3;1:3 [placebo QHS: ORMD-0801 QHS; placebo BID: ORMD-0801 BID; placebo TID: ORMD-0801 TID]).

An additional 75 subjects will be randomized to Cohort B and receive one of 5 treatment regimens (1:1:1:1): excipient matched placebo QHS, ORMD-0801 8 mg QHS, ORMD-0801 8 mg BID, ORMD-0801 16 mg QHS, or ORMD-0801 16 mg BID. Randomization will be in block sizes of 5 (1:1:1:1:1 [excipient matched placebo QHS: ORMD-0801 8 mg QHS: ORMD-0801 8 mg BID: ORMD-0801 16 mg QHS: ORMD-0801 16 mg BID]).

The randomization will be centralized and stratified by a) Sulfonylurea usage and b) whether they are on metformin alone or metformin plus one or 2 additional oral antidiabetic drugs at Screening. This will help ensure balanced treatment distribution of the subjects across the strata.

The additional 20 subjects in Cohort A who will receive excipient-matched placebo will not be randomized.

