	In the first two weeks of active treatment (Part 1) subjects will receive double-blind therapy according to their randomized regimen (ORMD-0801 8 mg or 16 mg, or excipient matched placebo) to be taken QHS or BID. Subjects will then enter Part 2 at the same dose and regimen administered in Part 1. Part 2:
	During Part 2, subjects will remain on fixed doses of ORMD-0801 (or placebo) for 10 weeks. Doses will not be adjusted unless clinically indicated for adverse events or hypoglycemia. Overall glycemia will be measured by A1C at baseline and over 12 weeks of treatment.
	Additional measures will include fasting plasma glucose (FPG) drawn at clinic visits, outpatient SMBG values and adverse events recorded in the diary. Subjects will undergo blinded continuous glucose monitoring (CGM) for 2 weeks at baseline (on at Visit 1, off at Visit 3) and end-of-study (on at Visit 8, off at Visit 9). Standardized Mixed Meal Tolerance Testing (MMTT) will be performed at baseline (Visit 3) and at end-of-study (Visit 9). A1C will also be measured at intervals.
	Throughout the 12-week treatment period, subjects will be monitored and may be considered for "rescue" in case of persistent symptomatic hyperglycemia (see Rescue Criteria) to restore adequate glycemic control.
Primary Endpoint	 Mean change in HbA1C from baseline to Week 12 (Visit 9, Part 2 Week 10) of the treatment period.
Secondary Endpoints	 Means and mean changes from baseline over time for HbA1C and FPG. Change from baseline to Week 12 (Visit 9, Part 2 Week 10) in postprandial glucose (PPG) parameters during a MMTT, including AUC₀₋₆₀, AUC₀₋₁₂₀, and 1 & 2-hour PPG absolute levels and excursions.
	 Changes from baseline in glycemic parameters measured using outpatient CGM. Change in weight from baseline to Week 12 (Visit 9, Part 2 Week 10) of the treatment period. Proportion of subjects requiring glycemic rescue therapy during
	 the treatment period. Safety assessed by adverse event reporting including adverse events of special significance such as hypoglycemia.
Exploratory Endpoints	Patient reported outcomes, by Diabetes Treatment Satisfaction Questionnaire _{status} (DTSQ _s) and Questionnaire _{change} (DTSQc) score over 12 weeks.
Duration of Participation	Subjects will be evaluated for participation in the study during a 1 to 3-week Screening period. Following Screening, eligible subjects will

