- 4) ORMD-0801 16 mg twice daily BID: dosed in the evening prior to bedtime (@ 10 PM \pm 90 minutes) and 30-45 minutes prior to breakfast.
- 5) Excipient matched placebo once daily QHS: dosed in the evening prior to bedtime (@ $10 \text{ PM} \pm 90 \text{ minutes}$)

Part 1:

Cohort A

In the first two weeks of active treatment (Part 1) subjects will receive double-blind therapy according to their randomized regimen (placebo or ORMD-0801) to be taken QHS, BID or TID. Subjects will undergo a step-wise dose escalation from a starting dose of 16 mg (Visit 3), to 24 mg (Visit 4), to a top dose of 32 mg (Visit 5 onward). Subjects will then enter Part 2.

Cohort B

In the first two weeks of active treatment (Part 1) subjects will receive double-blind therapy according to their randomized regimen (ORMD-0801 8 mg or 16 mg, or excipient matched placebo) to be taken QHS or BID. Subjects will then enter Part 2 at the same dose and regimen administered in Part 1.

Part 2:

During Part 2, subjects will remain on fixed doses of ORMD-0801 (or placebo) for 10 weeks. Doses will not be adjusted unless clinically indicated for adverse events or hypoglycemia. Overall glycemia will be measured by A1C at baseline and over 12 weeks of treatment.

Additional measures will include fasting plasma glucose (FPG) drawn at clinic visits, outpatient SMBG values and adverse events recorded in the diary. Subjects will undergo blinded

continuous glucose monitoring (CGM) for 2 weeks at baseline (on at Visit 1, off at Visit 3) and end-of-study (on at Visit 8, off at Visit 9). Standardized Mixed Meal Tolerance Testing (MMTT) will be performed at baseline (Visit 3) and at end-of-study (Visit 9). A1C will also be measured at intervals.

Throughout the 12-week treatment period, subjects will be monitored and may be considered for "rescue" in case of persistent symptomatic hyperglycemia (see Rescue Criteria) to restore adequate glycemic control.

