3.4.1 Visit 3 (Part 1 Week 0 ± 3 days)

Subjects will report to the clinic in the morning following a 10-hour fast prior to taking morning medications and the following procedures will be performed:

• Review of prior and current medications and supplements;

- Review inclusion and exclusion criteria;
- Physical examination;
- Measurement of weight;
- Measurement of vital signs (SBP/DPB and heart rate);
- Remove CGM device and download the data.
- Collect and review the paper diary for completeness of entries.
- Collection of fasted blood and urine samples for:
 - o Clinical safety labs, including hematology, serum chemistry (with FPG and A1C), and urinalysis (see Section 6.1.5 for list of tests);
 - o Urine drug screen;
 - o Urine pregnancy test (WCBP only);
- Perform MMTT test:
 - o No therapy is given prior to the baseline MMTT test.
 - Collection of blood samples for insulin, glucose, and C-peptide analysis prior to the start of the MMTT test at -50 and -5 minutes (See section 6.2.1).
 - Additional blood samples will be drawn at 60 and 120 minutes (±10 minutes) post-prandially to obtain insulin and glucose levels. The exact time of the blood draw, even if it falls outside of the defined window, is to be recorded on the eCRF.
 - Blood samples for C-peptide will also be drawn at 60 minutes.
- Cohort A: Subjects will be randomized to double-blind placebo or ORMD-0801 QHS, BID, or TID, which will begin at Visit 3.
 - Subjects randomized to placebo will be randomized to receive placebo QHS, BID, or TID and follow the same corresponding dosing schedule shown below for ORMD-0801.
 - o Subjects randomized to ORMD-0801 QHS will be instructed to take one dose at bedtime (@ 10 PM ±90 minutes, each night no sooner than 2 hours after dinner).
 - Subjects randomized to ORMD-0801 BID will be instructed to take one dose at bedtime (@ 10 PM ±90 minutes, each night no sooner than 2 hours after dinner) and one dose 30-45 minutes prior to breakfast.
 - Subjects randomized to ORMD-0801 TID will be instructed to take one dose at bedtime (@ 10 PM ±90 minutes, each night no sooner than 2 hours after dinner), one dose 30-45 minutes prior to breakfast, and one dose 30-45 minutes prior to lunch.
- Cohort B: Subjects will be randomized to double-blind excipient matched placebo QHS, ORMD-0801 8 mg QHS, ORMD-0801 8 mg BID, ORMD-0801 16 mg QHS, or ORMD-0801 16 mg BID, which will begin at Visit 3.

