 - O Subjects randomized to ORMD-0801 8 mg QHS will be instructed to take one dose at bedtime (@ 10 PM \pm 90 minutes, each night no sooner than 2 hours after dinner).
 - Subjects randomized to ORMD-0801 8 mg BID will be instructed to take one dose at bedtime (@ 10 PM ±90 minutes, each night no sooner than 2 hours after dinner) and one dose 30-45 minutes prior to breakfast.
 - O Subjects randomized to ORMD-0801 16 mg QHS will be instructed to take one dose at bedtime (@ 10 PM ± 90 minutes, each night no sooner than 2 hours after dinner).

- Subjects randomized to ORMD-0801 16 mg BID will be instructed to take one dose at bedtime (@ 10 PM ±90 minutes, each night no sooner than 2 hours after dinner) and one dose 30-45 minutes prior to breakfast.
- O Subjects randomized to excipient matched placebo QHS will be instructed to take one dose at bedtime (@ $10 \text{ PM} \pm 90 \text{ minutes}$, each night no sooner than 2 hours after dinner).
- Subject training on medication dosing.
- Review e-diary for completeness of entries, SMBG data and hypoglycemic events.
- Collect unused placebo and review e-diary for compliance.
- Provide subjects with SMBG, nutrition, and hypoglycemic symptom training.
- Record adverse events.
- Remind subjects to collect 7-Point SMBG profiles.
- Remind subjects to arrive fasting for Visit 4.

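### Cohort B is described as double-blind, but its only placebo arm is once daily at bedtime, so the dosing schedule identifies all 30 BID subjects as on active drug

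*Combined protocol and SAP*

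**What the plan says.** **Blinding claim.** Section 3.1 (and the synopsis) says of Cohort B in Part 1 that "subjects will receive double-blind therapy according to their randomized regimen (ORMD-0801 8 mg or 16 mg, or excipient matched placebo"; the Visit 3 text in Section 3.4.1 says "Cohort B: Subjects will be randomized to double-blind excipient matched placebo QHS, ORMD-0801 8 mg QHS, ORMD-0801 8 mg BID". Section 5.3.1.2 describes all subjects in Part 1 as receiving double-blind treatment.

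**Arms.** Section 5.2 says "An additional 75 subjects will be randomized to Cohort B and receive one of 5 treatment regimens (1:1:1:1): excipient matched placebo QHS". The four-part ratio there is a slip for five arms, since the block definition reads "Randomization will be in block sizes of 5 (1:1:1:1:1 [excipient matched placebo QHS: ORMD-0801 8 mg QHS" and goes on to list the remaining three. The synopsis, Section 3.1, Section 3.4.1 and Section 5.2 all list the same five arms, with one placebo arm, at bedtime.

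**Dosing times.** In Section 3.4.1, "Subjects randomized to excipient matched placebo QHS will be instructed to take one dose at bedtime". Both active QHS arms have the same instruction. The 8 mg BID and 16 mg BID arms add a dose before breakfast.

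**Cohort A, for contrast.** Section 5.2 masks active versus placebo from subjects, investigators, monitors and "staff members responsible for treating and evaluating subjects, but the treatment regimen will be unblinded". The blind survives there because "Subjects randomized to placebo will be randomized to receive placebo QHS, BID, or TID and follow the same corresponding dosing schedule".

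**Text that points the other way.** The synopsis and Section 3.1 describe Cohort B treatment as "ORMD-0801 8 mg or 16 mg, or excipient matched placebo) to be taken QHS or BID". Section 5.1 allows the single Cohort B capsule in a dose to be placebo where blinding needs it. Section 6.2.1 gives subjects a morning study dose before the meal test without limiting it by regimen, and Table 1 footnote 5 also refers to double-blind medication before the final meal test. Section 3.5.4 restricts that dose to the BID and TID arms.

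**The concern.** A double-blind claim for active versus placebo requires that nothing visible to subject or assessor settles which one the subject has. In Cohort B, dosing frequency is visible: kit labels carry directions for use (Section 5.1.1), dosing times are entered in a diary that site staff review (Section 6.3), and the Visit 9 pre-meal dose depends on the regimen (Section 3.5.4). If frequency alone settles the question for the BID arms, the stated property does not hold for them.

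The outcomes open to influence are those that rest on judgement: rescue, which is at the investigator's discretion (Section 3.7); adverse event reporting and causality (Sections 7.5 and 7.6); and the DTSQ questionnaires. A report that presented BID versus placebo on these as a double-blind comparison would be inaccurate.

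**Working it through.** **Inputs.** Section 8.2.2: 75 subjects for 60 completers; 15 per arm for 12 completers; five arms. Section 5.2: equal allocation in blocks of 5, one of them placebo QHS; Cohort A in blocks of 12, placebo to active 1:3 within each regimen. Section 3.4.1: dosing times by arm. The 20% drop-out rate is stated for Cohort A (Section 8.2.1); Cohort B's figures imply the same.

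**1. The plan's own figures.** 60 / (1 − 0.20) = 75; 12 / (1 − 0.20) = 15; 5 × 15 = 75. All reproduce.

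**2. Subjects by visible schedule.**
- Bedtime only: placebo, 8 mg QHS, 16 mg QHS = 3 × 15 = 45, of whom 2 × 15 = 30 are active.
- Bedtime plus pre-breakfast: 8 mg BID, 16 mg BID = 2 × 15 = 30, all active.

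**3. Chance of active drug given the schedule.**
- Cohort B BID: 30/30 = 100%.
- Cohort B QHS: 30/45 = 66.7%.
- Cohort A, any regimen: 3 of 4 in each block, 9 of 12 overall = 75%. The schedule tells the observer nothing.

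**4. Share affected.** 30/75 = 40% of Cohort B. Active subjects are 4 × 15 = 60, so 30/60 = 50% of them. Expected BID completers are 2 × 12 = 24 of 60.

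**5. Does any other text restore the blind?**
- The words allowing QHS or BID after the placebo (synopsis, Section 3.1) have no matching arm in any list and no slot in the block.
- The Section 5.1 allowance concerns the capsule within a dose. It adds no dosing time, and the Section 3.4.1 instructions give QHS subjects no morning dose.
- The meal-test dose is a single clinic administration, described inconsistently across Sections 3.5.4 and 6.2.1 and Table 1 footnote 5. It is not a daily dummy.

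**6. What stays masked.** Each Cohort B dose is one capsule of 8 mg or 16 mg, so the strengths remain masked within QHS and within BID, assuming the two strengths look alike. Section 5.1 describes placebo as matching the product in appearance. Among the QHS arms, active versus placebo remains masked.

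**7. With uniform dosing times.** If all five arms had the same visible schedule, the chance of active drug would be 60/75 = 80% for everyone, and no subject would be identifiable.

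**The case against.** The strongest reply is that the protocol may intend a dummy dose. A single-capsule Cohort B dose needs no padding to make up 8 mg or 16 mg, so the Section 5.1 allowance could mean a whole placebo dose, and the meal-test text does not fit a strictly bedtime placebo arm. This is fair as evidence that the documents conflict. It does not restore the blind, because sites following Section 3.4.1 would give no morning capsule to QHS subjects.

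The second reply is that little depends on it, and most of this stands. Section 8.1 names no Cohort B comparison. HbA1C is measured by a central laboratory (Section 6.1.5) and CGM is blinded (Section 3.1). Rescue is only counted (Section 8.4), with numeric FPG criteria alongside the discretion. No inferential adverse event comparison is planned (Section 8.6.2), events are elicited with non-leading questions (Section 7.5), and the DTSQ is exploratory (Section 8.5).

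Three stronger readings might be inferred, and the documents do not support them:
- **The BID arms are open-label.** They are not: the 8 mg versus 16 mg contrast remains masked.
- **The primary result is compromised.** Cohort B is not named in the stepwise test, and Cohort A has placebo in every regimen. Section 8.1 does not say whether Cohort B subjects could be pooled into its BID or combined placebo groups, so this rests on their not being named.
- **Causality grading and the stopping rule are distorted.** The grade definitions in Section 7.6 refer to active drug, but its opening sentence asks about study treatment whether active or placebo. Section 7.5.2 already breaks the blind for medical emergencies and for unexpected, possibly related serious events, which would cover many Grade 4 events. An influence on the initial judgement is possible; neither its direction nor its size can be derived.

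**Conclusion.** The point holds. As written, Cohort B is not blinded to active versus placebo in its two BID arms: 30 subjects, 40% of the cohort and half of its active subjects. Everything else in the Cohort B blind is intact.

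This rests on the arm lists and dosing instructions being complete, and on the observer knowing the arms. Site staff have the protocol. Whether subjects know depends on consent text that is not available here, so the effect on DTSQ is less certain than that on rescue and adverse event judgements.

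The error is in a stated design property and in what BID versus placebo results may be said to show. It is not a threat to the stated confirmatory sequence. It should be corrected, because the correction is specific and nearly free.

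**What to change.** 1. In Sections 3.1, 3.4.1, 5.2 and 5.3.1.2, state that the Cohort B BID arms are dose-blinded but not blinded to active versus placebo.
2. Limit double-blind active versus placebo conclusions in Cohort B to the QHS arms. Report BID versus placebo rescue, adverse event and DTSQ results as not masked to active versus placebo.
3. Reconcile three items with the arm list: the QHS-or-BID wording in the synopsis and Section 3.1, the placebo-capsule allowance in Section 5.1, and the meal-test dose text in Section 3.5.4, Table 1 footnote 5 and Section 6.2.1.

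The cost is wording, plus loss of the double-blind label for BID versus placebo. Sample size, blocks and arms are unchanged.

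**Optional, for the sponsor to decide.** If a no-insulin dummy capsule that makes dosing times uninformative is intended or preferred, Sections 3.4.1 and 5.2 should say so and state which of the two placebos in Section 5.1 it contains. It would apply to 3 × 15 = 45 subjects for 12 × 7 = 84 days, so 45 × 84 = 3,780 extra capsules at full adherence with no drop-out. The downside is extra fish-oil or excipient exposure in those 45 subjects. The choice of content also affects what the arm contrasts mean, since Section 8.5 itself sets out to compare the two placebos.

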- 17. Subject is a user of recreational or illicit drugs or has had a recent history (within 1 year of Screening) of drug or alcohol abuse or dependence. (Note: Alcohol abuse includes heavy alcohol intake as defined by >3 drinks per day or >14 drinks per week, or binge drinking) at Screening. Occasional intermittent use of cannabinoid products will be allowed provided that no cannabinoid products have been used during the 1 week prior to each visit.
- 18. One or more contraindications to metformin as per local label.
- 19. History of gastrointestinal disorders (e.g. hypochlorhydria) with the potential to interfere with drug absorption.
- 20. At the Principal Investigator's discretion, any condition or other factor that is deemed unsuitable for subject enrollment into the study.

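### Section 5.2 prints fixed block sizes and their composition in the protocol investigators hold, while the dosing regimen is visible: a small, avoidable weakness in allocation concealment

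*Combined protocol and SAP*

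**What the plan says.** Section 5.2 gives both blocking schemes in full. For Cohort A: "Randomization will be in block sizes of 12 (1:3;1:3;1:3", with one placebo to three active in each of QHS, BID and TID. For Cohort B: "Randomization will be in block sizes of 5 (1:1:1:1:1", one slot per arm. Active versus placebo is double-blind in Cohort A, "but the treatment regimen will be unblinded".

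Cohort B has no such sentence, but its schedule shows the regimen. In Section 3.4.1 the only placebo is taken once at night ("Subjects randomized to excipient matched placebo QHS will be instructed to take one dose at bedtime"). The two BID arms add a dose before breakfast, and no dummy morning dose is described for QHS subjects.

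Section 5.2 also says that allocation runs through a central IWRS, stratified by sulfonylurea use and by background oral therapy. Section 8.3 names different strata (Screening HbA1C and current treatment regimen). Neither section lists site. The synopsis title calls the study multi-center, and the documents do not give the number of sites.

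Eligibility is reviewed again at Visit 3, the randomisation visit (Section 3.4.1 and Table 1). The last exclusion criterion in Section 4.2 lets the investigator exclude for "any condition or other factor that is deemed unsuitable for subject enrollment into the study".

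**The concern.** Each investigator signs to confirm that they understand the protocol, so each has the block size and contents. Counting visible regimens within a block shows what remains, and late in a block the next regimen may be certain. Blinding of active versus placebo does not prevent this, because the regimen itself is not hidden.

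What is at stake is allocation-dependent enrolment. A person who expects a particular regimen could let that affect the discretionary eligibility decision at Visit 3, or the timing within its three-day window either way. In Cohort A, placebo subjects in the same regimen would not fully cancel such selection. Section 8.1 compares each active regimen, starting with TID, with placebo pooled over all three regimens. One third of that pooled placebo is TID and two thirds is QHS or BID.

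**Working it through.** **Inputs.** From Section 5.2: blocks of 12 and 5 and their composition; 265 subjects randomised in Cohort A and 75 in Cohort B; central allocation without site strata. Assumptions: 1 to 30 equal sites, because the number is not stated; 3 or 5 equal strata, depending on whether one and two add-on drugs are separate levels (metformin alone excludes sulfonylurea use).

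**The plan's own figure.** Three regimens × (1 placebo + 3 active) = 12 slots: 3 placebo, 3 QHS, 3 BID and 3 TID active. This reproduces the stated result, "Therefore the overall randomization will be 1:1:1:1". By visible regimen, a Cohort A block is 4 QHS, 4 BID and 4 TID. A Cohort B block is 3 QHS and 2 BID.

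**Upper bound: an observer who sees the stratum's whole sequence.** The next regimen is certain when all *m* remaining slots share one regimen. For block size *n* with *c_r* slots of regimen *r*, P(certain, *m* left) = Σ_r C(*c_r*, *m*) / C(*n*, *m*).

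- Cohort A: *m* = 1: 1; *m* = 2: 18/66 = 0.273; *m* = 3: 12/220 = 0.055; *m* = 4: 3/495 = 0.006. The sum is 1.333, and 1.333/12 = 11.1% of allocations.
- Cohort B: *m* = 1: 1; *m* = 2: (3 + 1)/10 = 0.4; *m* = 3: 1/10 = 0.1. The sum is 1.5, and 1.5/5 = 30% of allocations.
- Cohort B split: certainly BID (0.4 + 0.1)/5 = 10%; certainly QHS (0.6 + 0.3 + 0.1)/5 = 20%.
- Best guess, by exact enumeration: Cohort A 51% correct against 33% by chance; Cohort B 72% against 60% from always guessing QHS.

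**One site's view of central blocks.** A simulation spread subjects at random over equal sites and strata, and let each site know where every block starts, which is generous to the observer. Share of allocations with a certain regimen (ranges cover 3 and 5 strata):

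| Equal sites | Cohort A | Cohort B |
|---|---|---|
| 1 | 10.1–10.5% | 26.8–28.1% |
| 2 | 0.04% | 5.6–5.9% |
| 5 | about 0 | 0.7–0.8% |
| 10 | about 0 | 0.2% |
| 30 | about 0 | 0.02–0.03% |

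The one-site row falls a little short of 11.1% and 30% because the last block in a stratum may be incomplete. Simple guessing from a site's own counts is right about 38% of the time in Cohort A with 2 sites, 35% with 5 to 10, and 34% with 20 to 30, against 33% by chance. In Cohort B, with 2 or more sites, it is right 55–58% of the time, which is worse than always guessing QHS (60%).

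**What a correct prediction reveals.** In Cohort A allocation is "1:3 (placebo:ORMD-0801) within each of those regimens at Visit 3", so the chance of active treatment is 3/4 whichever regimen is predicted. In Cohort B, BID is certainly active, and QHS is active with probability 2/3.

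**Effect of larger blocks, whole sequence seen and block size known.** Going from 12 to 24 in Cohort A lowers certainty from 11.1% to 5.9%. Going from 5 to 10 in Cohort B lowers it from 30.0% to 17.7%. Varying undisclosed sizes would also hide the block boundaries; that further gain was not calculated.

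**The case against.** The strongest reply is that central allocation through an IWRS without site strata is already the main protection. The 11% and 30% describe an observer whom the protocol does not give to any enrolling investigator. That stands, and it is why those figures are upper bounds. It does not cover a site that enrols most of a stratum. Nor does it cover staff who may see several sites: Section 12.1 has study monitors reviewing eCRFs and drug accountability, although the protocol gives them no part in enrolment.

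A second reply is that small fixed blocks protect balance. This also stands, especially in Cohort B, with 15 subjects per arm (Section 8.2.2) and on average 75/3 = 25 or 75/5 = 15 subjects per stratum.

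A reader might infer three stronger things, none of which the documents support:

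- **That investigators can in practice foresee the next allocation.** This would need one person to see nearly all of a central block within a stratum.
- **That the TID test is biased.** Selection by regimen could unbalance TID, BID or QHS against pooled placebo. Bias would also need a correct prediction, a motive, and a slot not taken meanwhile by another site. No size or direction is shown. The ANCOVA in Section 8.3.1 adjusts for baseline HbA1C and additional antidiabetes drugs, which limits selection on those variables only.
- **That the blocks unblind Cohort B.** Every BID subject is known to be on active drug because placebo is given QHS only. That would remain under any blocking scheme. Block size affects only whether BID can be foreseen.

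**Conclusion.** The point holds as a cheap improvement of low priority. Fixed block sizes and compositions are disclosed to investigators while the regimen is visible, and no stated purpose requires the disclosure. With the whole sequence in view, the regimen is certain for 11% of Cohort A and 30% of Cohort B allocations. For a single site with two equal sites this falls to about 0.04% and 6%, and with five or more to about 0 and under 1%. The single-site figures assume equal sites drawing at random from central blocks. They would be too low if one site dominated a stratum, if sites shared allocations, or if blocks were in practice held by site. No internal contradiction in the blocking scheme and no failed test follows from this point.

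**What to change.** - Delete the block sizes and compositions from Section 5.2 and keep only the allocation ratios. The Cohort B ratio is first printed there with four terms for five arms, so correct it in the same edit.
- Put the block details in a randomisation specification with restricted access.
- Have the IWRS vary block sizes modestly within strata, for example 12 and 24 in Cohort A and 5 and 10 in Cohort B.
- State that blocks are held centrally, not by site.

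Cost: a new list in the existing IWRS and a short wording change. The downside is slightly more possible imbalance within a stratum when the last block is unfinished. A block of 5 holds one subject per arm and a block of 10 holds two, so the largest gap between two Cohort B arms in an unfinished block rises from 1 to 2. In Cohort A, counting all placebo as one arm, it rises from 3 to 6 (three per arm in 12, six in 24). This matters mainly in Cohort B, where strata are small. The change does not restore blinding of the Cohort B BID arms.
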